15.2. E-DIARY COMPLIANCE

The flow of the eDiary entries patient has to follow is:

1. E-RS
2. Study medication compliance
3. Background medication compliance (if applicable)
4. Rescue medication use

Based on this, we can assess if patient has been compliant with their E-RS questions, based on their study medication compliance and therefore no further E-RS compliance needs to be assessed.

15.2.1. DERIVATIONS

E-diary compliance will be calculated as per the following. Use study day assigned to determine the date for each week, as per the windowing conventions described in section 6.4 of the SAP:

$$\frac{(\text{Week X}^* < \text{number of days study medication data was entered in the e - Diary} \leq \text{Week Y})}{[\text{Study Day at Week Y}] - [\text{Study Day at Week X}] + 1} * 100$$

*If Week X = Day 1, update “<” to be “≤”.

16. EFFICACY OUTCOMES

16.1. PRIMARY EFFICACY

[figure not shown]
The primary efficacy analysis will be performed for the mITT population.

16.1.1. PRIMARY EFFICACY VARIABLE & DERIVATION

The primary efficacy variable is change from baseline in FEV₁ AUC_{0-12h} at Week 12. FEV₁ data captured in the eResearch Technology (ERT) database will be used for the model in determining baseline value and for AUC calculation.

16.1.1.1. AUC_{0-T}

Spirometry (FEV₁) will be performed at Screening and the following time points during, each treatment:

- Day 1: ≤40 minutes pre-dose (2 measurements); 30 minutes, 1, 2 and 4 hours post-dose.
- Week 6 and Week 24: ≤40 minutes pre-dose; 30 minutes, 1, 2 and 4 hours post-dose.
- Week 12 and Early Termination: ≤40 minutes pre-dose; 30 minutes, 1, 2, 4, 6, 8 and 12 hours post-dose.

Baseline FEV₁ is the mean of the two measurements taken before study medication on the day of first dosing, i.e. ≤40 minutes pre-dose on Day 1.

The average effect will be calculated as the AUC divided by the length of the time interval of interest (for example, 12 hours for AUC_{0-12h} or 4 hours for AUC_{0-4h}). AUC will be calculated using the trapezoidal method, as follows:

$$AUC = \frac{1}{2} \sum_{i=1}^{n-1} (T_{i+1} - T_i)(C_{i+1} + C_i)$$

Where T_i is the ith time value, C_i is the ith effect value, n is the number of time values. The change from the baseline FEV₁ to average FEV₁ (AUC) will be summarized and analyzed. If two last data points are missing the AUC is set to missing, that is for AUC_{0-12h} we require at least up to 8 hours of assessments and for AUC_{0-4h} we require at least up to 2 hours of assessments. This would mean if we only have 8 hours of assessments, then we would calculate AUC_{0-8h}, however it would still be labelled as AUC_{0-12h}. If there is no pre-dose measurement available for the calculation of the AUC, then the AUC will not be calculated. The pre-dose measurement used in the calculation of AUC is the latest value measured ≤40 minutes pre-dose. The pre-dose value will be used as time 0 when computing AUC_{0-T}. For AUC_{6-12h} we require at least the 6-hour and 12-hour timepoint for analysis.

16.1.2. MISSING DATA METHODS FOR PRIMARY EFFICACY VARIABLE

The main analysis for the primary endpoint will include estimates from missing data imputation described below. This is done to investigate the influence of missing data due to drop-outs. Only patients with non-missing baseline will be included in the analysis.

The primary analysis will be analyzed using MI based on the missing data assumption Missing at Random (MAR). This process will follow four steps:

1. Partially impute the data for a monotone missing pattern with 100 as a number of imputations and “20905” as seed number. Employ the Markov Chain Monte Carlo (MCMC) method with treatment, region, background medication strata, smoking strata, baseline FEV₁ and average FEV₁ AUC_{0-12h} at Week 12.

The following SAS codes will be used:

```
proc mi data=<data1> out=<data2> nimpute=100 seed=20905;
```

```
var <treatment> <region> <BackgroundMedStrata> <SmokingStrata>
  <baseline> <visits>;
mcmc impute=monotone chain=multiple;
run;
```

2. Impute the monotone data using a regression imputation model. Apply by imputation using seed number “20905” with treatment, region, background medication strata, smoking strata, baseline FEV₁ and average FEV₁ AUC_{0-12h} at Week 12.

The following SAS codes will be used:

```
proc mi data=<data2> out=<dataout> nimpute=1 seed=20905;
  by _imputation_;
  class <treatment> <region> <BackgroundMedStrata>
    <SmokingStrata>;
  var <treatment> <region> <BackgroundMedStrata>
    <SmokingStrata> <baseline> <visits>;
  monotone regression;
run;
```

3. Each multiple imputed dataset in Step 2 will be analyzed separately, as described in section 16.1.3 of the SAP.
4. The estimates (LS means, SE, CI, and p-value) from the model analysis in Step 3 will be combined using Rubin’s combination rules for statistical inference.

Sensitivity analysis will be done using:

- Average imputation will be based on data collected on treatment at required visit, or at early termination visit. This will be done on patient level. If there is no such data available, impute with average change from baseline for the particular visit in the opposite randomized treatment group.
- Tipping point approach will repeat the ANCOVA analysis, under Missing not at Random (MNAR) assumption, to assess the robustness of p-value significance. In case the original analysis will produce a p-value<0.05, then the imputed values will be adjusted by a value k (positive) added or subtracted (depending on what worsens the endpoint) to the endpoint of the patients in Ensifentrine group (worsening results) and added or subtracted (depending on what improves the endpoint) from the endpoint of the patients in placebo group (improving results). The value for k is determined by adjusting the bias starting with a value of 0.01 and increasing it with increments of 0.01 until p-value obtained from MI method is no longer statistically significant (p-value>0.05). Seed number used will be the same as for MI analysis, “20905”. If the primary analysis is not significant (p-value>0.05), then the tipping point is reversed by determining value for k by adjusting the bias until p-value≤0.05. If the p-value<0.05 with more improvement in the placebo group comparably

to Ensifentrine group, then the tipping point is reversed by adjusting until there will be no more treatment difference between groups.

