2.5. ESTIMANDS

The primary and secondary estimands to support regulatory decisions are described in Table 1.

Table 1: List of Estimands

		Attributes			
Estimand	Definition	Population	Variable/ Endpoint	Intercurrent event handling strategy	Population-level summary measure
Primary	The efficacy of ensifentrine on lung function compared to placebo over a 12-hour dosing interval in patients with moderate to severe COPD.	Patients with moderate to severe COPD aged 40-80 years (inclusive) that are in the modified intent-to-treat (mITT) population. See full list of inclusion and exclusion criteria in sections 5.1, 5.2 and 5.3 of study protocol.	Change from baseline forced expiratory volume in 1 second (FEV ₁) to average FEV ₁ area under the curve over 12 hours (AUC _{0-12h}) at Week 12.	Regardless of whether the patient discontinues treatment prematurely and regardless of major protocol deviation, as per the Treatment Policy strategy.	Estimated treatment difference at Week 12 of the double-blind period (and corresponding 95% confidence interval [CI]) from analysis of covariance (ANCOVA) analysis.
Secondary	To evaluate the effect of ensifentrine on other lung function parameters.	Patients with moderate to severe COPD aged 40-80 years (inclusive) that are in the mITT population. See full list of inclusion and exclusion criteria in sections 5.1, 5.2 and 5.3 of study protocol.	
 Change from baseline FEV₁ to average FEV₁ AUC_{0-4h} at Week 12 Change from baseline FEV₁ to peak FEV₁ at Week 12 Change from baseline FEV₁ to morning trough FEV₁ at Week 12 	Regardless of whether the patient discontinues treatment prematurely and regardless of major protocol deviation, as per the Treatment Policy strategy.	Estimated treatment difference at Week 12 of the double-blind period (and corresponding 95% CI) from ANCOVA analysis.

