4.2. INTERIM ANALYSIS

There is no interim analysis planned for this study, however additional patients may be randomized if:

- the SD has increased significantly from the estimated 250 mL, as per sponsor discretion, and/or
- the withdrawal rate at 24 weeks exceeds 25% overall, and the percentage of patients with missing FEV₁ over 12 hours at Week 12 in mITT (modified Intent-to-Treat) population exceeds 20% overall.

Note: As part of the primary endpoint analysis, SD of the treatment difference is calculated to check the sample size with 90% power.

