16.1.3. PRIMARY ANALYSIS OF PRIMARY EFFICACY VARIABLE

The primary objective of this study is to test the hypothesis that there is a difference between ensifentrine in comparison with placebo.

The change from baseline FEV₁ to average FEV₁ AUC_{0-12h} will be compared between ensifentrine and placebo using ANCOVA with fixed effects for treatment, region, background medication strata and smoking strata and baseline FEV₁ as covariate. Missing data will be imputed using imputation described in section 16.1.2 of the SAP. The estimated treatment difference will be presented with 95% CI and associated p-value. Furthermore, SD will be presented for the treatment difference to check the sample size with 90% power. Summary statistics will be performed on the imputed values.

Model assumptions will be tested as per the following rules on the blinded data, before the DBL.

1. Residual vs Predicted plots will be created to check residuals are uncorrelated and normally distributed.
2. Normality of the data will be checked using Kolmogorov-Smirnov normality test.

If any of the checks specified above fail the test, then alternative approaches will be discussed, including different ways of transposing data. The SAP will be updated to reflect any changes prior to DBL.

Only spirometry measurements with best test review (BTR) grades “Acceptable” and “Borderline Acceptable” are used in the analysis and baseline calculations.

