16.1.4. SENSITIVITY ANALYSIS OF PRIMARY EFFICACY VARIABLE

The primary endpoint will be presented for the following:

- Subgroup analysis will be performed by subgroups, including data imputation described in sections 7.5 and 16.1.2 of the SAP, respectively.
- Observed data analysis will be performed by the following subgroups:
 - Analysis with no data imputation, including all patients with data collected, on treatment or not, and at required timepoint or at EOS visit (excluding patients with missing data).
 - Analysis with no data imputation, including only patients with data collected at the

required visit while still on randomized treatment at scheduled visit, or at end of study visit within the visit window.

- Average imputation, as described in section 16.1.2 of the SAP.
- Analysis with tipping point approach, as described in section 16.1.2 of the SAP.
- Analysis with multiple imputation, as described in sections 16.1.2 and 16.1.3 of the SAP, based on PP population.

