16.2.2. MISSING DATA METHODS FOR SECONDARY EFFICACY VARIABLES

16.2.2.1. MI method – continuous data

The analysis for key secondary endpoints (FEV₁ AUC_{0-4h}, peak FEV₁, morning trough FEV₁, SGRQ total score and weekly mean E-RS total score) and for evening trough FEV₁ and weekly rescue medication will be performed using MI based on the missing data assumption MAR.

This process will follow four steps (below the example uses baseline FEV₁, but it is repeated also for baseline of other key secondary endpoints mentioned above, excluding the ones evaluated weekly):

1. Partially impute the data for a monotone missing pattern with 100 as a number of

imputations and “20905” as seed number. Employ the Markov Chain Monte Carlo (MCMC) method with treatment, region, background medication strata, smoking strata, baseline FEV₁ and <Visit data>. <Visit data> corresponds to all scheduled visits available for the parameter analyzed. Each visit will correspond to a covariate within the model.

The following SAS codes will be used:

```
proc mi data=<data1> out=<data2> nimpute=100 seed=20905;
  var <treatment> <region> <BackgroundMedStrata> <SmokingStrata>
  <baseline> <visits>;
  mcmc impute=monotone chain=multiple;
run;
```

2. Impute the monotone data using a regression imputation model. Apply by imputation using seed number “20905” with treatment, region, background medication strata, smoking strata, baseline FEV₁ and <Visit data>.

The following SAS codes will be used:

```
proc mi data=<data2> out=<dataout> nimpute=1 seed=20905;
  by _imputation_;
  class <treatment> <region> <BackgroundMedStrata>
  <SmokingStrata>;
  var <treatment> <region> <BackgroundMedStrata>
  <SmokingStrata> <baseline> <visits>;
  monotone regression;
run;
```

3. Each multiple imputed dataset in Step 2 will be analyzed separately, as described in section 16.2.3 of the SAP.
4. The estimates (LS means, SE, CI and p-value) from the model analysis in Step 3 will be combined using Rubin’s combination rules for statistical inference.

Note: For secondary endpoints that are evaluated weekly, the following updates will be implemented for the first 2 steps:

1. MI model will contain weekly means at all weeks available to impute the data to create a monotone missingness pattern, so will be imputed missing values at any week (i.e Week 1, Week 2, etc.).

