16.2.4. SENSITIVITY ANALYSIS OF SECONDARY EFFICACY VARIABLES

For the key secondary endpoints, the following sensitivity analysis will be performed at Week 12.

Subgroup analysis as specified in section 7.5 of the SAP.

- ANCOVA analysis with average imputation, as described in section 16.2.2 of the SAP.
- ANCOVA analysis with MI, only considering baseline and Week 12 (for lung function parameters) in the imputation model, as described in section 16.1.2 and 16.1.3 of the SAP.
- ANCOVA analysis with MI using the range data method as described in section 16.2.2.3 for SGRQ total score and weekly mean total E-RS.
- Tipping point approach, as described in section 16.1.2 of the SAP.
- Analysis with MI method, as described in sections 16.2.2 and 16.2.3 of the SAP, based on PP population.

For FEV₁ key secondary endpoints (FEV₁ AUC_{0-4h}, peak FEV₁, morning trough FEV₁) additional sensitivity analysis will be performed:

- MMRM model with treatment, visit and treatment by visit as fixed effect; baseline as covariate; patient as random factor; unstructured covariance by visit. If the model does not converge a compound symmetry covariance structure will be used. Kenward-Roger method will be used to estimate the model degrees of freedom. weeks.

For weekly mean E-RS total score and SGRQ total score, additional analysis will be performed:

- For weekly mean E-RS total score at 6, 12 and 24 weeks, using ANCOVA approach, as described in section 16.2.3 of the SAP, all patients with baseline weekly mean = 0 will be excluded.
- For SQRG total score at 6, 12 and 24 weeks, using ANCOVA approach, as described in section 16.2.3.1 of the SAP, all patients with baseline assessment done after dosing time and date will be excluded.

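### The primary imputation model contains only the ANCOVA terms, so it reproduces the observed-data ANCOVA; FEV₁ already collected could be added as auxiliary variables for a modest gain

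*SAP*

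**What the plan says.** **Imputation model.** SAP 16.1.2 specifies 100 imputations under missing at random: an MCMC step to reach a monotone pattern, then a regression step. Both run "with treatment, region, background medication strata, smoking strata, baseline FEV₁ and average FEV₁ AUC_{0-12h} at Week 12". The code has a generic visits placeholder, but the text fills it only with Week 12 AUC0-12h. The same section states: "Only patients with non-missing baseline will be included in the analysis".

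**Analysis model.** SAP 16.1.3 compares the arms "using ANCOVA with fixed effects for treatment, region, background medication strata and smoking strata and baseline FEV₁ as covariate".

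**No-imputation analysis.** The first observed-data analysis in SAP 16.1.4 is "Analysis with no data imputation, including all patients with data collected, on treatment or not, and at required timepoint or at EOS visit".

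**When AUC0-12h is missing.** Under SAP 16.1.1.1 it is not calculated if the pre-dose value is absent, and it is set to missing if the last two time points are absent. Under SAP 6.4, for patients who leave the study, an end-of-study AUC0-12h up to Day 95 counts as Week 12. Under SAP 7.3, off-treatment data are used.

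**Secondary lung-function endpoints.** In SAP 16.2.2.1 the visit data entered in the imputation "corresponds to all scheduled visits available for the parameter analyzed". SAP 16.2.4 lists as a sensitivity analysis an "ANCOVA analysis with MI, only considering baseline and Week 12 (for lung function parameters) in the imputation model".

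**Protocol.** Section 9.4.1 bases the imputation for the primary endpoint on baseline characteristics and leaves further detail to the SAP.

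**The concern.** Imputation can improve on the observed-data analysis only if it uses information that the analysis model lacks. Here it uses none. The missing-at-random assumption is then conditional on baseline and strata alone, although most patients without a Week 12 AUC0-12h will have post-dose FEV₁ from Day 1, and many from Week 6. Some will have most of a Week 12 curve. At stake are some precision, a stronger missing-data assumption than the data require, and the reading of 16.1.4: agreement between the primary result and the first no-imputation analysis would be close to automatic and should not be taken as evidence of robustness.

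**Working it through.** **1. The plan's own figure.** Protocol 9.2 gives SD 250 mL, 500 vs 300 evaluable, two-sided 5%, and 90% power for 59 mL. SE₀ = 250 × √(1/300 + 1/500) = 18.26 mL. Power = Φ(59/18.26 − 1.96) = 89.8%, so the figure is reproduced.

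**2. Why the imputation returns the ANCOVA.** Assume treatment, region and strata are recorded for everyone; baseline is complete by rule. The pattern is then already monotone, and the MCMC step has nothing to impute. Let X be the ANCOVA design and b_obs the fit to patients with an observed outcome. The regression step draws missing outcomes around X_mis·b_obs. Averaged over draws, the completed-data fit is

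(X′X)⁻¹(X_obs′y_obs + X_mis′X_mis·b_obs) = (X′X)⁻¹(X_obs′X_obs + X_mis′X_mis)·b_obs = b_obs.

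Imputing AUC and analysing change from baseline makes no difference to the treatment coefficient, because baseline is in both models.

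**3. Check by simulation.** 500 vs 300 patients, SD 250 mL, true difference 59 mL, 10% or 20% missing, 100 imputations, Rubin's rules, 250 trials per setting. Imputation minus observed-data ANCOVA: mean gap at most 0.07 mL, per-trial SD 0.6–1.0 mL, SE ratio 1.000–1.003, correlation at least 0.998. In one dataset with 5,000 imputations, the imputation gave 59.40 (SE 20.98) and the ANCOVA 59.43 (SE 21.01).

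**4. What is left unused.** SAP 16.1.1.1 schedules FEV₁ at 0.5, 1, 2 and 4 h, with a pre-dose value, at Day 1, Week 6 and Week 24. At Week 12 the trapezoid weights at 0, 0.5, 1, 2, 4, 6, 8 and 12 h are 0.0208, 0.0417, 0.0625, 0.125, 0.1667, 0.1667, 0.25 and 0.1667. A missing pre-dose value (2.1% of the weight) voids the whole AUC. A curve that stops at 6 h is also voided, although the 0–6 h points carry 58.3%. The documents do not say how often this happens.

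**5. Precision.** With missing fraction d (at random) and residual correlation ρ between the auxiliaries and the outcome,

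SE = SE₀ × √[(1 − ρ²)/(1 − d) + ρ²], power = Φ(59/SE − 1.96).

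The documents give no ρ; 0.5 to 0.8 is assumed. The 20% level is taken from SAP 4.2, where one condition for randomising more patients is that "the percentage of patients with missing FEV₁ over 12 hours at Week 12 in mITT (modified Intent-to-Treat) population exceeds 20% overall". It is a trigger, not an expected rate; 10% is an assumed lower level.

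| Missing | ρ | SE (mL) | Power at 59 mL |
|---|---|---|---|
| 10% | 0 (present) | 19.25 | 86.6% |
| 10% | 0.5 / 0.7 / 0.8 | 19.00 / 18.77 / 18.62 | 87.4 / 88.2 / 88.7% |
| 20% | 0 (present) | 20.41 | 82.4% |
| 20% | 0.5 / 0.7 / 0.8 | 19.90 / 19.39 / 19.06 | 84.3 / 86.1 / 87.2% |

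Simulation with a Week 6 auxiliary (20% missing, ρ 0.7) agrees: the SE falls from 20.47 to 19.43 mL.

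**6. Bias of the present imputation.** All mechanisms here are assumed.
- Dropout depends on Week 6 FEV₁ equally in both arms (20% missing, ρ 0.7): mean estimate 58.6 mL against a true 59, so bias is under 1 mL.
- 15% missing in one arm and 25% in the other, dropout related to Day 1 or Week 6 response (log-odds slope 0.5–1.0 per SD, correlation 0.5–0.7): 5.8–14.4 mL in either direction if no dropout has a usable early-termination AUC, and 2.3–5.4 mL if half do.
- 7.5% and 12.5%: 2.9–7.4 mL and 1.3–3.2 mL.

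Auxiliaries remove nearly all of this bias in the simulation, but by construction, because dropout was generated from those auxiliaries.

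**The case against.** **The secondary imputation is no precedent.** SAP 16.2.2.1 uses all visits of the same parameter. AUC0-12h is scheduled only at Week 12 or early termination, so that rule applied literally gives 16.1.2. Protocol 9.4.1 also separates the primary endpoint from those assessed repeatedly. This stands. A reader might infer that the SAP breaks its own method or the protocol; it does neither. The secondary imputation is an analogy, and borrowing related FEV₁ variables is an extension of it.

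**The code may intend more.** The placeholder is plural, and an MCMC step would be idle under the reading given here. Even so, the text of both steps names only Week 12 AUC0-12h.

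**Much is already covered.** Off-treatment and early-termination curves count as Week 12 values, and there are on-treatment observed-data, opposite-arm, tipping-point and per-protocol analyses. This narrows the point to patients who still have no AUC0-12h. The imputation is also not pointless, since the tipping-point analysis needs its imputed values. The SAP never calls the first no-imputation analysis an independent check. None of these analyses changes the primary estimate.

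**The gain is small if the effect is larger than 59 mL.** Protocol 2.2 reports 87 mL at Week 4 for 3 mg added to tiotropium. At 87 mL and 20% missing, power is Φ(87/20.41 − 1.96) = 98.9% now and 99.2–99.5% with auxiliaries (SE 19.90 to 19.06). This stands.

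**A biased primary result?** A reader might infer this, since a simulation with dropout tied to Week 6 FEV₁ mainly in placebo (20% missing, ρ 0.7) pulls the mean estimate to 25.8 mL. That is an extreme assumed mechanism with no early-termination curves credited. The documents give no dropout pattern to support it.

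**Conclusion.** The primary imputation is equivalent to the all-observed-data ANCOVA, and the first no-imputation analysis in 16.1.4 therefore repeats it. That follows from the listed terms and needs no dropout assumption beyond recorded strata and region. It is consistent with protocol 9.4.1 and is a free improvement, not an error. The expected benefit is modest: 0.5–1.3 mL off the SE and about 2–5 points of power at 59 mL with 20% missing, and less at 10%. Those figures rest on assumed missing rates, correlations and missingness at random. A bias correction of any size depends on differential, response-related dropout without a usable early-termination AUC, which is possible but unknown.

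The auxiliaries do not settle a further question raised by the treatment-policy estimand in SAP 2.5, which applies "Regardless of whether the patient discontinues treatment prematurely and regardless of major protocol deviation, as per the Treatment Policy strategy". On-treatment FEV₁ does not by itself recover off-treatment outcomes. Adding on/off-treatment status by arm is a separate trade-off, since in simulation it could raise the SE by up to about 1.8 mL when few off-treatment curves are observed. It is not part of this point.

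**What to change.** Before unblinding, amend SAP 16.1.2:

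- Extend the VAR lists in steps 1 and 2, in time order ahead of Week 12 AUC0-12h, with Day 1 AUC0-4h, Week 6 trough, Week 6 AUC0-4h, and the Week 12 post-dose values at 0.5, 1, 2, 4 and 6 h as separate variables. Week 24 AUC0-4h may follow. Separate time points are needed because Week 12 AUC0-4h is itself not calculated when the pre-dose value is absent.
- State the order, since monotone regression depends on it.
- State that when an early-termination curve supplies the Week 12 AUC0-12h, its points are not also entered as Week 6 auxiliaries. Under SAP 6.4, a curve up to Day 53 could otherwise fill both roles. A large-sample check found under 0.4 mL of residual bias from this, so it is a matter of clear specification.
- Keep the present imputation as a sensitivity analysis, next to the tipping-point and opposite-arm analyses.

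The cost is a short SAP revision and longer variable lists in the code. No new data, visits or patients are needed.
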